## **STUDY PROTOCOL. Elkar laguntza**

### AIMS

The general aim of the present research will be to evaluate the effectiveness of a peer social support intervention in cancer patients at the Onkologikoa Foundation of Guipuzcoa. Specifically, the immediate and long-term effect that such intervention will have on symptoms of psychological distress, quality of life, coping strategy, perception of social support, perception of the disease and emotional regulation will be evaluated. As a secondary aim of this study, we intend to evaluate the immediate and long-term effect of the peer social support intervention on the immune system (through the determination of the levels of cytokines IL-1 $\beta$ , IL-2, IL-6, IL-8, IL-10, IFN- $\gamma$  and TNF- $\alpha$ ), on the monoaminergic system (through the determination of plasma levels of serotonin, tyrosine, phenylalanine, tryptophan, quinurenine, quinurenic acid and 3-HK), on the HPA axis (through the measurement of the diurnal cycle of cortisol), and on sex hormones (through the measurement of estradiol and testosterone levels), systems that have been related both to the development of anxious-depressive symptoms and to the development, progression and recurrence of cancer.

In addition, it will be studied at what time the application of the program is most effective, being applied in newly diagnosed patients (experimental group 1) and in patients who have just finished medical treatment (experimental group 2).

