For each GE1 patient, a specific volunteer will be selected based on the patient's tumor type and medical treatment, although depending on the availability of volunteers, other variables will also be taken into account: age, preferred language, time availability, partner, children and socioeconomic level. Once selected, each patient and volunteer will be given a letter of introduction to the other, in order to learn basic information about the patient before the first session. The social peer support program will begin the week prior to the start of medical treatment. There will be a total of eight sessions, one every fifteen days approximately, for a total duration of four months. The duration of each session will be as follows: the first and second sessions will last approximately one hour, the following sessions will last an average of 30 minutes. Patients and volunteers will be given the possibility to request a change of person in case they feel that the bond between them is not adequate.

Once the support program has been completed in EG1, a second evaluation of clinical, psychological and biological variables will be carried out, and, in addition, satisfaction with the intervention program will be evaluated, thanks to the Treatment Satisfaction Questionnaire. In GE2, the evaluation of clinical, psychological and biological variables will be carried out four months after the first evaluation. A third evaluation of all participants will be carried out 15 days after receiving the news of the end of the medical treatment (chemotherapy or radiotherapy). At four months and eight months after the end of medical treatment (chemotherapy or radiotherapy), the fourth and fifth evaluations will be carried out. In each of these evaluations the procedure will be as follows: each participant will be given a questionnaire of psychological measures to fill in before their appointment and four saliva collection tubes, which they will have to collect the day before their appointment. In addition, they will be scheduled for a blood draw and for the collection of the questionnaires and saliva samples.

GE2 patients will participate in the peer support program, but the application of this intervention will take place 15 days after receiving the news of the end of medical treatment. The intervention in this group will have the same characteristics and the same evaluations as those of GE1.

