#### DATA ANALYSIS

The relationships between the variables collected will be analyzed with the SPSS version 22.0 statistical package and with the JMP 10 statistical package. In all the analyses performed, the following variables will be controlled: type and duration of medical treatment and pharmacological treatment. Repeated measures analyses will be performed to study the effect of the intrasubject support program. Also, in order to study the possible physiological and psychological differences between experimental groups 1 and 2, analysis of variance (ANOVA) will be carried out. Pearson's correlation coefficient will be used to analyze the relationships between the different physiological and psychological variables considered in this study. Several General Linear Models (GLM) analyses will be performed to determine the predictive value of each of the variables in the possible benefit obtained after the application of the program. To study the interactions in each of the GLM analyses performed, a simple regression analysis will be carried out.

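### Effectiveness rests on six unranked psychological domains, and the documents name no deciding outcome, evaluation or contrast, no significance level and no multiplicity control

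*Combined protocol and SAP*

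**What the plan says.** **Aims.** The AIMS section of the combined protocol and SAP sets effectiveness as the general aim and specifies it as "the immediate and long-term effect that such intervention will have on symptoms of psychological distress, quality of life, coping strategy, perception of social support", followed by illness perception and emotional regulation. That makes six psychological domains in one list. The only ranking is that biological outcomes fall under a secondary aim; nothing orders the six. A separate question is added: "it will be studied at what time the application of the program is most effective".

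**Schedule.** METHODS gives a baseline and four later evaluations. Evaluation 2 follows the end of the programme in EG1, and for the other group (also written GE2): "In GE2, the evaluation of clinical, psychological and biological variables will be carried out four months after the first evaluation". The programme's length is given as: "There will be a total of eight sessions, one every fifteen days approximately, for a total duration of four months". For evaluation 3: "A third evaluation of all participants will be carried out 15 days after receiving the news of the end of the medical treatment". For the second group's programme: "GE2 patients will participate in the peer support program, but the application of this intervention will take place 15 days after receiving the news". Evaluations 4 and 5 come four and eight months after medical treatment ends.

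**Analysis.** DATA ANALYSIS plans two analyses that bear on the programme's effect: "Repeated measures analyses will be performed to study the effect of the intrasubject support program" and "in order to study the possible physiological and psychological differences between experimental groups 1 and 2, analysis of variance (ANOVA) will be carried out". All analyses are to control for type and duration of medical treatment and for pharmacological treatment. Correlations, general linear models and simple regressions are also planned. VARIABLES lists the questionnaires without marking one scale or score as deciding.

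**The concern.** Each method has a stated purpose, but the plan does not say which result, in which domain and at which evaluation, would lead to the programme being called effective. The open choices also answer different questions:

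- A group difference at evaluation 2 compares programme with no programme yet.
- A group difference at evaluation 4 or 5 compares early with late support, because EG2 has started by then.
- A within-subject change has no concurrent control, so it mixes any programme effect with the ordinary course of diagnosis, treatment and recovery.

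With these choices open, any of three results could be presented as the answer to the general aim: one selected domain out of six, a before-after change, or a late group difference that is really about timing. The chance of a false claim would then depend on a decision made after the data are seen.

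**Working it through.** **The plan's own figure.** The only design figure is 120 patients. It comes without significance level, power, effect size, SD or dropout, so it cannot be reproduced and points to no deciding outcome.

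**1. Error rate if any one domain suffices (illustration).**
Inputs: six domains (AIMS). Assumed, because the documents give none: two-sided 0.05 per test, no true effect, one evaluation, one contrast, and a claim if any domain is significant.

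- Independent tests: 1 − 0.95^6 = 1 − 0.735 = 0.265.
- Equally correlated tests: write each statistic as √ρ·U + √(1−ρ)·E, with U shared and E specific to the domain. Integrate over U the probability that all six stay within ±1.96, and subtract from 1. This gives 0.207 at ρ = 0.5 and 0.164 at ρ = 0.7.
- If all six had to be significant, the rate would be at most 0.05.

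**2. What each evaluation can show.**
Assumptions: 30-day months, and the news arrives when treatment ends. T is treatment length in days; g is the number of days from evaluation 1 to the start of treatment. The documents give neither.

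- *Evaluation 2.* EG2's evaluation is on day 120 after evaluation 1, and its programme starts on day g + T + 15. The programme starts first if T < 105 − g: 98 days for g = 7, 75 days for g = 30. With longer treatment, evaluation 2 is a clean comparison of programme with no programme yet.
- *Evaluation 3.* This evaluation and the start of EG2's programme are both placed 15 days after the news, with no order given. Whether EG2 is still unsupported at evaluation 3 is therefore unsettled.
- *Evaluation 4.* It falls about day 120 after treatment ends. EG2 starts on day 15, and eight sessions span 105 days (7 intervals of 15) to 120 days (four months), so its programme ends on day 120 to 135. Evaluation 4 is at or before that end.
- *Evaluation 5.* It falls about day 240, after both programmes are complete. Time since the last session still differs between groups.

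**3. What one primary test could detect.**
Two-sample t-test, 80% power, unadjusted, 1:1 allocation assumed from the balanced blocks. The normal approximation is d = (z for alpha + 0.842) × √(2/n).

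| Test | n per arm | Normal approximation | t-test |
|---|---|---|---|
| Primary, 0.05 | 60 | 2.802 × 0.1826 = 0.51 SD | 0.52 SD |
| Primary, 0.05 | 45 (assumed 25% dropout) | 2.802 × 0.2108 = 0.59 SD | 0.60 SD |
| Strictest Holm step, five secondary domains, 0.05/5 = 0.01 | 60 | 3.418 × 0.1826 = 0.62 SD | 0.63 SD |

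**The case against.** The strongest reply is that the structure is implicit rather than absent. METHODS ties evaluation 2 to the end of EG1's programme and sets a parallel EG2 assessment, which is recognisably the supported versus not-yet-supported comparison. It also calls the trial a crossover and says EG2 has the same evaluations, so evaluations 3 and 4 look like EG2's before and after measures. This stands, and a reader who inferred that the design has no programme versus no-programme comparison would be wrong. What remains is that DATA ANALYSIS attaches neither the ANOVA nor the repeated-measures analysis to an evaluation and ranks neither above the other.

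A reader might also take 26% as this trial's false-positive rate. The documents do not support that, because they state no level and no claim rule, and an all-six rule would hold the rate at or below 5%. Nor should the count simply be multiplied by evaluations: six domains at four evaluations is 24 tests, or 1 − 0.95^24 = 71% if independent. The plan does not commit to a separate test at each visit, and one repeated-measures test per domain would reduce the count.

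Finally, it would go too far to say that a planned result could not be told from a selected one. The domains and schedule are written down, so an omitted result could be noticed. The point is limited to these documents; a primary outcome may be named elsewhere.

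**Conclusion.** The point holds, and the plan should be changed. Effectiveness is to be judged across six equally ranked domains, four post-baseline evaluations and two kinds of contrast. These documents do not say which of them decides, at what level, or with what control of multiple testing. The error rate of an effectiveness claim is therefore not fixed in them.

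The size can only be illustrated: 16% to 26% under the assumed any-one-domain rule at one evaluation. The change of question across evaluations needs no such assumption about levels or rules. By evaluations 4 and 5 EG2 has also started, so a group difference there concerns timing. Evaluation 4 is not a clean timing comparison either, because on the stated schedule it falls at or before the end of EG2's programme. Confidence is high on the gap itself and moderate on its practical size.

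**What to change.** Add to DATA ANALYSIS, before any data are seen, wording such as:

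> Effectiveness will be judged on one primary outcome, contrast and time point: HADS total score, EG1 versus EG2 as randomised, at evaluation 2, adjusted for baseline HADS, two-sided 0.05. The other five psychological domains at evaluation 2 are secondary, Holm-adjusted. Within-subject repeated-measures analyses and group comparisons at evaluations 3, 4 and 5 are secondary and cannot alone support an effectiveness claim. Evaluation 4 will be described as taken at or before the end of EG2's programme (about day 120 against day 120 to 135 after treatment ends, if the news comes at that time), so evaluation 5 is the timing comparison with both programmes complete. Biological outcomes, correlations and predictor models are exploratory. The number of EG2 patients who started the programme before evaluation 2 will be reported.

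The sponsor may choose another single domain or score. The text should also state how type and duration of medical treatment and pharmacological treatment enter the primary model. METHODS should state the order of evaluation 3 and EG2's first session.

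**Cost.** Wording only: no change to visits or sample size. The headline claim would rest on one domain at one time point, with the detectable differences shown above (0.52 SD at 60 per arm, 0.60 SD at 45; 0.63 SD at 60 per arm for the strictest secondary step). If many EG2 patients start before evaluation 2, the primary contrast is diluted, which is why their number should be reported.

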### METHODS

The present project will consist of a longitudinal clinical trial to evaluate the effectiveness of a peer social support intervention in cancer patients at the Onkologikoa Foundation of Guipuzcoa.

The intervention will consist of 8 face-to-face peer social support sessions conducted by volunteers diagnosed with various types of cancer who have finished their medical treatment (chemotherapy, radiotherapy, surgery) or who have been in a stable phase for at least two years and who are motivated to participate in this type of intervention. These people will initially be informed through informative meetings or through letters sent by e-mail by professionals from the Onkologikoa Foundation and the Osakidetza Active Patient program and, afterwards, they will be referred to the program coordinator [name] for a series of evaluations with the aim of checking whether these people have an adequate physical and mental recovery and that participation in the program will have the minimum psychological impact on them. Thus, the medical history will be checked and the following psychological variables will be evaluated: personality (through the Big-5 Inventory Short Version questionnaire), coping style (through the COPE-28 questionnaire), presence of anxious-depressive symptoms (through the Hospitalary Anxiety and Depression Scale questionnaire), resilience (through the resilience questionnaire) and emotional regulation (through the Emotion Regulation Questionnaire).

The selected individuals will participate in a training program conducted by experts in the field, including psychologists, physicians and oncologists, in which lectures, group work and role playing will be conducted under the supervision of the researchers. The main topics covered

during the program will include: cancer diagnosis and treatment, management and prevention of side effects, healthy habits, emotional intelligence, empathy and communication skills, among others. All volunteers will be informed of the importance of confidentiality of patient information.

Each of the volunteers will have to be with 2 or 3 patients at the same time since some authors state that performing support to more than one patient can compensate for a poor relationship with another patient, as well as serve as support in the event of a patient's death (Moulton et al., 2013). The volunteer-patient sessions will be conducted in rooms set up for this purpose in the Carlos Santamaría building of the UPV/EHU. After each session with the patients, each volunteer will have to attend an individual session with the program coordinator [name] to discuss their emotions and reactions after performing the intervention. Psychological supervision of the volunteers is a fundamental part of avoiding retraumatization and the possible appearance of anxious-depressive symptoms (Giese-Davis et al., 2006). Likewise, volunteers will have to participate in group sessions every two months with the rest of the volunteers and the program coordinator [name] in order to strengthen group cohesion, resolve doubts, detect needs and carry out the necessary training.

The patients in this study will be 120 patients with various types of cancer from the Onkologikoa Foundation. Each patient will be matched with a volunteer depending on the type of tumor and medical treatment, since some authors state that for the support program to be effective, the volunteers must have had the same type of tumor and medical treatment as the patients (Pistrang et al., 2012). This is why it will be necessary to homogenize the group of volunteers as much as possible so that the sample of patients has as little variability as possible. The inclusion criteria are: having received the diagnosis of cancer in the last month; not having started medical treatment; the tumor type and medical treatment coinciding with any of the volunteers. The exclusion criteria are: relapse; suffering or having suffered from a serious mental disorder (according to DSM-V criteria). The recruitment of these patients will take place just after the diagnosis, and the professionals of the Onkologikoa Foundation will be in charge of offering this type of intervention to the patients who meet the inclusion criteria of the study.

Those patients who are interested in participating will be informed about the present research project by the coordinator of the program and by the members of the research team of the Onkologikoa Foundation and it will be these same people who will be in charge of giving the information sheet and the informed consent, and of summoning each participant for the collection of data for the first evaluation. Each participant will be given an evaluation questionnaire of sociodemographic, clinical and psychological variables that he/she will have to bring completed for the day of the appointment. Also, each participant will be given four saliva collection bottles, which they will have to collect four times the day before their appointment. The times of collection of these saliva samples will be upon waking up, 30 minutes later, before lunch (between 13:00 and 13:30) and before dinner (between 20:00 and 20:30). The saliva samples will be collected by the program coordinator at the Onkologikoa Foundation and will be coded and managed by the Biobanko. Subsequently, they will be taken to the Psychobiology laboratory of the UPV/EHU for the determination of different biological variables. In addition,

participants will have to undergo a blood draw on the day of the appointment. The blood collection will be performed by a nurse member of the research team of the Onkologikoa Foundation. The blood samples will be coded and managed by the Biobanko. Subsequently, they will be transferred to the Psychobiology laboratory of the UPV/EHU for the determination of different biological variables.

After this first collection of clinical, psychological and biological data, patients will be randomly selected, through a balanced block randomization method, to be part of the experimental group 1 (EG1) or the experimental group (EG2). As this is a crossover design clinical trial, patients in GE1 will start the peer social support program before the start of medical treatment, while patients in GE2 will start the peer social support program after the end of medical treatment.

For each GE1 patient, a specific volunteer will be selected based on the patient's tumor type and medical treatment, although depending on the availability of volunteers, other variables will also be taken into account: age, preferred language, time availability, partner, children and socioeconomic level. Once selected, each patient and volunteer will be given a letter of introduction to the other, in order to learn basic information about the patient before the first session. The social peer support program will begin the week prior to the start of medical treatment. There will be a total of eight sessions, one every fifteen days approximately, for a total duration of four months. The duration of each session will be as follows: the first and second sessions will last approximately one hour, the following sessions will last an average of 30 minutes. Patients and volunteers will be given the possibility to request a change of person in case they feel that the bond between them is not adequate.

Once the support program has been completed in EG1, a second evaluation of clinical, psychological and biological variables will be carried out, and, in addition, satisfaction with the intervention program will be evaluated, thanks to the Treatment Satisfaction Questionnaire. In GE2, the evaluation of clinical, psychological and biological variables will be carried out four months after the first evaluation. A third evaluation of all participants will be carried out 15 days after receiving the news of the end of the medical treatment (chemotherapy or radiotherapy). At four months and eight months after the end of medical treatment (chemotherapy or radiotherapy), the fourth and fifth evaluations will be carried out. In each of these evaluations the procedure will be as follows: each participant will be given a questionnaire of psychological measures to fill in before their appointment and four saliva collection tubes, which they will have to collect the day before their appointment. In addition, they will be scheduled for a blood draw and for the collection of the questionnaires and saliva samples.

GE2 patients will participate in the peer support program, but the application of this intervention will take place 15 days after receiving the news of the end of medical treatment. The intervention in this group will have the same characteristics and the same evaluations as those of GE1.

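### The trial is a randomised immediate-versus-delayed-start design, not a crossover: evaluations 4 and 5 compare early with delayed support, so they cannot show an effect against no support or separate timing from recency

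*Combined protocol and SAP*

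**What the plan says.** AIMS sets two goals that bear on this point. One is to evaluate "the immediate and long-term effect that such intervention will have on symptoms of psychological distress" and on other outcomes. The other is a timing question: "it will be studied at what time the application of the program is most effective".

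METHODS randomises 120 patients in balanced blocks to two arms, written there as EG1 or GE1 and EG2 or GE2 (EG1 and EG2 below). It labels the design: "As this is a crossover design clinical trial, patients in GE1 will start the peer social support program before the start of medical treatment". For EG1, "The social peer support program will begin the week prior to the start of medical treatment". On length: "There will be a total of eight sessions, one every fifteen days approximately, for a total duration of four months". For EG2, "the application of this intervention will take place 15 days after receiving the news of the end of medical treatment".

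All participants have evaluation 3 at that same 15-day point. Then: "At four months and eight months after the end of medical treatment (chemotherapy or radiotherapy), the fourth and fifth evaluations will be carried out".

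DATA ANALYSIS lists within-subject repeated measures for the programme's effect and ANOVA for differences between the two arms. It adjusts for the type and duration of medical treatment and for drug treatment. It does not say which evaluation answers which aim, and it has no term for carryover, period or time since support.

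**The concern.** In a crossover each patient is observed under both conditions, in an order set by randomisation, and the effect of the first condition is expected to have gone before the second is measured. Here each arm receives the programme once and neither arm is left without it. EG1 after its programme could stand for no support only if its benefit had vanished, which is the opposite of the long-term effect that the trial hopes to find.

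The last evaluation at which EG2 is still unsupported is evaluation 3. After that, a difference between arms reflects early against delayed support. If the effect lasts, the arms could converge, and a group ANOVA at evaluation 4 or 5 could be read as no long-term effect. If it fades, EG2 could look better only because its support was more recent, and the trial could conclude that support works best after treatment. Either conclusion could arise with no true difference between the two timings.

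**Working it through.** **Inputs from METHODS.** EG1 starts 7 days before treatment (the week prior, read as 7 days). There are eight sessions about 15 days apart, over four months. EG2's start and evaluation 3 both come 15 days after news of the end of treatment. Evaluation 2 in EG2 is four months after evaluation 1. Evaluations 4 and 5 are four and eight months after treatment ends.

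**Assumptions.** Treatment lasts T days; the documents give no length, so 46 to 365 days is shown. The news comes on the day treatment ends. Four months is 122 days and eight months 244.

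**Programme length.** 8 × 15 = 120 days, about 3.9 months, which agrees with the stated four months. From first to last session is 7 × 15 = 105 days. Both readings are carried through.

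**Timeline, day 0 = start of treatment**

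| Event | Session count (105 days) | Four months (122 days) |
|---|---|---|
| EG1 programme ends | −7 + 105 = 98 | −7 + 122 = 115 |
| EG2 starts; evaluation 3 | T + 15 | T + 15 |
| EG2 programme ends | T + 15 + 105 = T + 120 | T + 15 + 122 = T + 137 |
| Evaluation 4 | T + 122 | T + 122 |
| Evaluation 5 | T + 244 | T + 244 |

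**Time since the programme ended**

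- Evaluation 4: EG2 122 − 120 = 2 days past, or 122 − 137 = 15 days short. EG1 is T + 24 or T + 7 days past.
- Evaluation 5: EG2 124 or 107 days past. EG1 is T + 146 or T + 129 days past.
- Gap between arms at both evaluations: (T + 120) − 98 = T + 22 days, and (T + 137) − 115 = T + 22 days. This is 68, 144, 205 and 387 days for T = 46, 122, 183 and 365.

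At any fixed treatment duration the gap is still T + 22 days and goes entirely with arm. Adjusting for duration, as DATA ANALYSIS plans, does not remove it.

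**Evaluation 3.** Its lag after EG1's programme is (T + 15) − 98 = T − 83 days, or (T + 15) − 115 = T − 100 on the four-month reading.

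| T (days) | Lag, session count | Lag, four months |
|---|---|---|
| 46 | −37 | −54 |
| 122 | 39 | 22 |
| 183 | 100 | 83 |
| 365 | 282 | 265 |

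For treatment shorter than 83 days (100 on the other reading), evaluation 3 comes before EG1 has finished.

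**Evaluation 2.** If evaluation 1 is on day −7 (assumed), EG2's evaluation 2 is on day 115. It precedes EG2's start only if T + 15 > 115, so T > 100. An earlier evaluation 1 lowers this threshold day for day. Evaluation 2 is thus a supported-versus-unsupported contrast unless treatment is short.

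**Group contrast at evaluation 4.** Assume an immediate effect d = 0.5 SD in both arms, no true timing effect, and that EG1 retains a fraction r. EG2's advantage is d(1 − r). The rejection rate assumes 60 per arm, SD 1, two-sided 5%.

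| r | EG2 advantage (SD) | Chance of a significant difference |
|---|---|---|
| 0 | 0.5 | 78% |
| 0.5 | 0.25 | 28% |
| 1 | 0 | 5% |

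At r = 1 both programmes work fully, and the test rejects only at its nominal rate.

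**Averaging over evaluations 2 to 5.** Under the same model, with one drop to the retained level and then no change, the EG1 advantages are:

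- r = 1: (0.5 + 0.5 + 0 + 0)/4 = 0.25 SD
- r = 0.5: (0.5 + 0.25 − 0.25 + 0)/4 = 0.125 SD
- r = 0: (0.5 + 0 − 0.5 + 0)/4 = 0

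The average favours early support whenever some benefit persists, because EG2 is unsupported at two of the four visits.

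**Matching on recency.** Setting EG1's gain at evaluation 2 against EG2's gain at evaluation 4 roughly aligns time since support. It does so by comparing the period around treatment with recovery afterwards, and EG2's change after evaluation 3 has no unsupported group to show natural recovery.

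**The case against.** A reader might infer that the plan uses EG1 as EG2's control, or pools the two periods. The documents say neither. The crossover label appears once and is followed at once by a clear account of early and late start, and DATA ANALYSIS names no crossover model.

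A reader might also infer that the trial will report a false null or a false preference for late support. That is too strong. The programme's effect is assigned to within-subject repeated measures, and no aim is tied to evaluation 4 or 5. If both arms improved and then converged, that analysis would show change over time. Its weakness is different: the change is not controlled for recovery. The errors are possible, not certain.

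Nor does the trial lack an unsupported comparator altogether. Evaluations 2 and 3 provide one by randomisation, subject to treatment length. The contrasts at evaluations 4 and 5 are also valid randomised comparisons of two strategies.

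Two limits on the figures stand. Treatment length is undocumented, so no single lag can be quoted for evaluation 3. On the four-month reading, EG2 has not quite finished at evaluation 4, so it is not strictly true that both arms have completed the programme by then. Neither limit restores a comparison with no support at evaluations 4 and 5.

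**Conclusion.** The point holds in this form. The design is a randomised immediate-versus-delayed start. After evaluation 3 no contrast in the plan can show an effect against no support. The group ANOVA at evaluations 4 and 5 cannot separate timing from recency, which differs between arms by treatment length plus about 22 days. With an assumed 0.5 SD effect and no timing effect, the evaluation 4 difference could lie anywhere from 0 to 0.5 SD in favour of EG2, depending only on how much benefit EG1 keeps.

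That EG2 is unsupported up to evaluation 3, and supported after it, follows from the schedule alone. The day counts rest on the assumed treatment length and on the news coinciding with the end of treatment. The SD figures and rejection rates are illustrations under assumed effects and equal arms. The point should be corrected, but it does not undermine the early randomised comparisons.

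**What to change.** - **METHODS, design sentence.** Replace crossover with randomised immediate-versus-delayed start.
- **AIMS, METHODS and DATA ANALYSIS, effect against no support.** Base it on EG1 versus EG2 at evaluation 2 (immediate) and evaluation 3 (later). Complete evaluation 3 in EG2 before the introduction letter and first session. Report any EG2 patient whose evaluation 2 falls after that first session.
- **Lag.** Report the time from the end of EG1's programme to evaluation 3. Make no lasting-effect claim for patients whose evaluation 3 comes before that end (treatment under about 83 days on the session count).
- **Evaluations 4 and 5.** State that they compare early with delayed support as strategies, that equality there is not evidence of no effect, and that a difference there does not separate timing from recency.
- **Within-subject change.** Do not present EG2's own before-after gain as a controlled effect.
- **Time-averaged contrast.** If one is reported over evaluations 2 to 5, call it a strategy comparison, note that it leans towards early support, and do not use it to say when the programme is most effective.
- **METHODS, schedule.** Reconcile EG2's start, the four-month length and the timing of evaluation 4.

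Every evaluation is kept. The cost is a narrower long-term and timing claim, plus a small scheduling constraint, because evaluation 3 and EG2's start now share the same 15-day point.
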